Inclusion/Exclusion Criteria: Eligibility and ineligibility criteria should be specific. Describe how eligibility will be determined and by whom. Changes to the eligibility criteria at a later phase of the research have the potential to invalidate the research.

Inclusion criteria will be the adolescents aged 13-17 years old with type 1 diabetes, at least 18 months post-diagnosis, parent reported moderate to no physical activity for adolescent, ability to complete measures and intervention program in English as well as access to broadband internet with a computer, tablet, or smartphone, and currently residing in and receiving healthcare in the United States. After 30 participants are enrolled into the study, inclusion criteria will also include that the adolescent is from a marginalized racial or ethnic group. Exclusion criteria will be ward of state, active psychosis, and/or severe medical or psychiatric illness that limit participation for the youth (including any contraindications for physical activity per parent report on the physical activity readiness questionnaire).

Eligibility will be determined during the recruitment process by the research team member using self-report of the parent and adolescent.

Inclusion of Minorities and Women: Describe efforts to include minorities and women. If either minorities or women are excluded, include a justification for the exclusion.

We will ensure representative inclusion of persons of color, women (13-17 years old), and people with socioeconomic disadvantage through our national recruitment method that includes recruitment in communities that share these characteristics. In addition, to ensure we are enrolling participants from minority groups, we will modify our eligibility criteria after we enroll 30 participants in the study, to enroll only persons of color.

Inclusion of Children: Describe efforts to include children. Inclusion is required unless a clear and compelling rationale shows that inclusion is inappropriate with respect to the health of the subjects or that inclusion is inappropriate for the purpose of the study. If children are included, the description of the plan should include a rationale for selecting or excluding a specific age range of children. When included, the plan must also describe the expertise of the investigative team in working with children, the appropriateness of the available facilities to accommodate children, and the inclusion of a sufficient number of children to contribute to a meaningful analysis relative to the purpose of the study. Provide target accrual for this population. Identify whether children are wards of the state. **If children are excluded** then provide appropriate justification.

We are specifically recruiting 60 adolescents aged 13-17 with type 1 diabetes due to the specific developmental challenges associated with disease management during this developmental period and the importance of this period for reducing future health disparities. We anticipate that 60 adolescents will provide sufficient power for examining effect size changes of the intervention (see analysis section).

Our team is uniquely suited to conduct this work as we have recently developed and tested both neural and self-report measures of learning for adolescents with type 1 diabetes and scalable physical activity interventions for youths. PI [name] is a child clinical health psychologist with over 15 years of training in working with adolescents with type 1 diabetes and other chronic diseases including online intervention research. We have not included children that are wards of the state in this study, this is an exclusion criteria. The challenges children that are wards of the state face around diabetes management make engagement in this intervention implausible.

For protocols including the use of an investigational drug, indicate whether women of childbearing potential have been included and, if not, include appropriate justification.

n/a

If HIV testing is included specifically for research purposes explain how the test results will be protected against unauthorized disclosure. Include if the subjects are to be informed of the test results. If yes, include the process and provision for counseling. If no, a rationale for not informing the subjects should be included.

Not applicable

Will the SONA Psychology Pool be utilized? Include documentation indicating permission to use this recruiting tool Yes No

FINANCIAL CONSIDERATIONS

Describe all potential research related expenses to subjects:

There is no expense to participant adolescents or their parents/guardians except for their time required to complete the study and the use of internet to complete the assessment and receive study messages.

Compensation for participation: Describe all plans to pay subjects, either in cash, a gift or gift certificate. Please note that all payments must be prorated throughout the life of the study. The IRB will not approve a study where there is only a lump sum payment at the end of the study because this can be considered coercive. The amount of payment must be justified. Clarify if subjects will be reimbursed for travel or other expenses.

Not applicable

All Adolescents will receive \$25 for the intake assessment and \$50 for the follow-up assessment on a study provided cash card or gift card. Adolescents in the control group will be provided an incentive for wearing their Garmin fitness activity tracker, \$.50/day up to \$42. Adolescents in the intervention group can earn up to \$430 for meeting physical activity goals as a part of the incentives program. This amount is common for incentives programs and meets Medicaid guidelines for \$500 in annual incentives.

Research Data Management Plan: The Research Data Management and Security Plan form must be completed. The form, along with guidance, can be found in our [forms library](#) and must be submitted with your initial application.

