****If genetic information is being collected, GINA language must be added to the consent form.**

*Deception typically involves withholding information from the potential subject and would require an alteration to the consent process.

Statistical Considerations: Delineate the precise outcomes to be measured and analyzed. Describe how these results will be measured and statistically analyzed. Delineate methods used to estimate the required number of subjects. Describe power calculations if the study involves comparisons. Perform this analysis on each of the primary and secondary objectives, if possible.

In aim 1, we assess the feasibility and acceptability of the Activate program as well as its preliminary efficacy on behavior-change skills (goal-setting and coping skill efficacy) and average daily active minutes. To assess acceptability of the Activate program we will examine participant engagement with the Activate program components, including behavior skill training sessions completed and physical activity goals met, as well as qualitative and quantitative participant feedback on their experience with the program at the end of treatment. A priori benchmarks for acceptability, indicating no further revision is needed will be greater than 80% of sessions completed and physical activity goals met as well as more than 80% of participants providing positive feedback regarding willingness to participate again.

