To assess the preliminary efficacy of the Activate program we will examine changes in proximal primary outcomes of goal-setting, coping skill efficacy, and average daily active minutes compared between treatment and control groups at baseline and the 12-week follow-up assessment. We will conduct multilevel models with baseline-residualized gain scores for outcomes to identify the effect size for the treatment program on each of the three primary outcomes. Each model will include the baseline outcome covariate as well as additional disease covariates including diabetes technology use and length of diagnosis. All participants will be used in analyses, with missing data addressed with full information maximum likelihood estimation. A power sensitivity function was generated wherein our pilot study analyses were used to determine expected effect sizes. Anticipated effect sizes based on our pilot work for between group differences in behavior-change skills and average daily active minutes are Cohen's d of 0.4 to 1.2. With 60 participants, we will have 80% power to detect a Cohen's d of .7, 60% power to detect a Cohen's d of .6, at 95% power to detect a Cohen's d of .8. Thus, we will be powered to detect all but the smallest of potentially meaningful effects found in our previous intervention pilot work.

In aim 2, we test the impact of the Activate program on secondary mechanisms of biobehavioral self-regulation systems and glycemic and cardiovascular disease risk outcomes closely linked with type 1 diabetes health disparities. To assess changes in putative mechanisms and secondary outcomes we will use baseline-residualized gain scores in multilevel models to identify the effect size for the treatment program on each of the secondary outcomes assessed for behavior regulation, distress, c-reactive protein, mean and variability in daily blood glucose, and cardiovascular disease risk score. For all analyses missing data will be addressed with full information maximum likelihood estimation. A power sensitivity function was generated wherein our pilot study analyses were used to determine expected effect sizes. Based on our pilot work we anticipate effect sizes from Cohen's d of .4 to .8 and thus with 60 participants, we will again have 80% power to detect a Cohen's d of .7, 60% power to detect a Cohen's d of .6, at 90% power to detect a Cohen's d of .8. We will be powered to detect all but the smallest of potentially meaningful effects found in our pilot work.

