Should any adverse events, unanticipated problems or reportable new information arise, the PI will contact the IRB according to the Adverse Event and Unanticipated Problems Reporting Policy using the UVM Reporting Form.

Withdrawal Procedures: Define the precise criteria for withdrawing subjects from the study. Include a description of study requirements for when a subject withdraws him or herself from the study (if applicable).

At any time, a participant can choose to withdraw from participation. We do not anticipate withdrawing any adolescent from the study but reserve the right to do so under unforeseen circumstances. These might include situations such as discovery of a medical problem indicating the adolescent should not participate in physical activities. If a participant is withdrawn or withdraws from participation their data will not be included in analyses.

Sources of Materials: Identify sources of research material obtained from individually identifiable human subjects in the form of specimens, records or data. Indicate whether the material or data will be obtained specifically for research purposes or whether use will be made of existing specimens, records or data.

All data is being collected solely for research purposes. Participants will provide dried blood spot assays, measurements of abdominal circumference and blood pressure as well as complete computerized self-report questionnaires. This data will be coded at the time of collection.

DRUG INFORMATION

Investigators are encouraged to consult the UVM Medical Center Investigational Pharmacy Drug Service ([name]) prior to finalizing study drug/substance procedures.

Drug (s)

Not applicable

Drug name – generic followed by brand name and common abbreviations. Availability – Source and pharmacology; vial or product sizes and supplier. If a placebo will be used, identify its contents and source.

Preparation: Reconstitution instructions; preparation of a sterile product, compounded dosage form; mixing guidelines, including fluid and volume required. Identify who will prepare.

Storage and stability – for both intact and mixed products.

Administration – Describe acceptable routes and methods of administration and any associated risks of administration.

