#### Statistical Analysis Plan:

To assess the preliminary efficacy of the Activate program we will examine changes in proximal primary outcomes of average daily active minutes compared between treatment and control groups at baseline and the 12-week follow-up assessment. We will conduct multilevel models with baseline- residualized gain scores for outcomes to identify the effect size for the treatment program on each on the primary outcome. All participants will be used in analyses, with missing data addressed using an intention-to-treat approach where missing data were included and given a zero. A power sensitivity function was generated wherein our pilot study analyses were used to determine expected effect sizes. Anticipated effect sizes based on our pilot work for between group differences in behavior-change skills and average daily active minutes are Cohen's  $d$  of 0.4 to 1.2. With 60 participants, we will have 80% power to detect a Cohen's  $d$  of .7, 60% power to detect a Cohen's  $d$  of .6, at 95% power to detect a Cohen's  $d$  of .8. Thus, we will be powered to detect all but the smallest of potentially meaningful effects found in our previous intervention pilot work.

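### Formal withdrawals drop out of all three acceptability benchmarks, so the 80% bars describe those who stayed and will tend to favour Activate

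*Protocol*

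**What the plan says.** Aim 1a in the protocol concerns acceptability. Statistical Considerations set the decision rule, beginning with engagement: "A priori benchmarks for acceptability, indicating no further revision is needed will be greater than 80% of sessions completed and physical activity goals met". A third bar, set in the same sentence, concerns how adolescents felt about the program: "as well as more than 80% of participants providing positive feedback regarding willingness to participate again". The feedback is described as "qualitative and quantitative participant feedback on their experience with the program at the end of treatment". The text does not say whether the percentages are taken over those randomised, retained or responding, or whether the session and goal figures are pooled or per person.

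Withdrawal Procedures in the protocol state: "If a participant is withdrawn or withdraws from participation their data will not be included in analyses". No exception is made for sessions, goals or feedback.

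Three other places bear on the point:

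- The Aim 1 efficacy paragraph of the protocol says "All participants will be used in analyses, with missing data addressed with full information maximum likelihood estimation".
- The SAP, which covers average daily active minutes and contains no acceptability analysis, has "missing data addressed using an intention-to-treat approach where missing data were included and given a zero".
- The protocol's answer on stopping rules, under Data Safety and Monitoring, allows recruitment to be paused and the intervention revised if patterns appear in attrition, feasibility or acceptability. It gives no threshold.

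**The concern.** The benchmarks are a decision rule: passing them means that the program is not revised. Withdrawal is one of the plainer signs that a program did not suit a participant. Yet under the stated rule a formal withdrawal takes that person's undone sessions and unmet goals out of the first two figures, and removes the person from the third. Separately, anyone not reached at 12 weeks gives no feedback, and the plan does not say whether such a person stays in the denominator.

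The result is a set of figures conditioned on retention. They can look good partly because the less satisfied have gone. The stopping-rule text shows that the investigators regard attrition as a signal about the program, but attrition enters none of the bars.

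**Working it through.** The 80% bar is a chosen threshold with no derivation, so there is no figure of the plan to reproduce. The check is how far the denominator alone moves the result.

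**Inputs**

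- 60 adolescents in two arms (protocol, Aim 1). The allocation ratio is not stated; 1:1 is assumed, giving 30 in Activate.
- 8 skills sessions (protocol, Intervention: Activate Program).
- Bar: strictly more than 80% (protocol, Statistical Considerations).
- Withdrawals w: no expected rate is given. The range 0 to 9 of 30 (0 to 30%) is assumed.

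**Willingness benchmark.** With m = 30 − w retained, the fewest positive answers that pass is the smallest whole number above 0.8m.

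| Withdrawn | Retained | Positives needed | Share of retained | Share of 30 randomised |
|---|---|---|---|---|
| 0 | 30 | 25 | 83.3% | 83.3% |
| 3 | 27 | 22 | 81.5% | 73.3% |
| 6 | 24 | 20 | 83.3% | 66.7% |
| 9 | 21 | 17 | 81.0% | 56.7% |

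With all 30 counted, 24/30 is exactly 80% and does not pass, so 25 are needed.

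Chance of passing, if each retained adolescent has an assumed 90% chance of a positive answer (binomial tail):

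- 3 withdrawals: P(X ≥ 22 of 27) = 95.3% on the retained denominator. P(X ≥ 25 of 27) = 48.5% on the all-randomised denominator, with absent answers counted as not positive.
- 6 withdrawals: P(X ≥ 20 of 24) = 91.5% on the retained denominator. The all-randomised bar cannot be reached, since at most 24/30 = 80% are positive.

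**Session benchmark (pooled).** Let retained participants complete a fraction c and withdrawn participants a fraction s. The figure over all randomised is ((30 − w)c + ws)/30. The retained-only figure exceeds it by w(c − s)/30, which is positive only when c > s.

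Taking c = 7/8 and s = 3/8 (both assumed), the retained-only figure is always 87.5%. Over all randomised:

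- w = 3: (27 × 7 + 3 × 3)/240 = 198/240 = 82.5%, pass.
- w = 4: (26 × 7 + 4 × 3)/240 = 194/240 = 80.8%, pass.
- w = 5: (25 × 7 + 5 × 3)/240 = 190/240 = 79.2%, fail.
- w = 6: (24 × 7 + 6 × 3)/240 = 186/240 = 77.5%, fail.

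With these rates the decision does not change at 10% withdrawal and does change at 20%. If instead the 24 stayers complete all 8 sessions and the 6 leavers 3, the figure is (192 + 18)/240 = 87.5%, which passes either way.

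**The case against.** A reader might infer that everyone who quits Activate disappears from the figures, so that each early stop raises the score. The documents do not support that. Withdrawal Procedures apply to those who withdraw or are withdrawn from participation. An adolescent who stops doing sessions or chasing goals but stays in the study remains in the data and lowers those two figures. The 12-week assessment carries no condition of having completed sessions, so that person can still give negative feedback.

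A reader might also infer that the error can only favour Activate. That is not established. The protocol names reasons for leaving that need have nothing to do with acceptability: a newly discovered medical problem, loss of internet, a change of guardian. Removing a well-engaged adolescent for such a reason lowers the retained-only session and goal figures.

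Three further objections have weight:

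- Read literally, someone who gives no feedback is not among those providing positive feedback, so the third bar may already count a silent participant against the program. This helps only for non-responders who stay in the study; the withdrawal rule still removes the rest.
- The stopping-rule text can trigger revision for attrition, so the bars are not the only route to it. But it has no threshold and cannot make a bar fail.
- The sizes rest on assumed inputs, and the zero chance of passing at 6 withdrawals follows from counting absent answers as not positive.

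The statements that all participants are analysed do not settle the matter. They sit with the efficacy models. Neither maximum likelihood estimation for a model nor a zero for missing active minutes fixes the denominator of an acceptability percentage. If they were held to override the withdrawal rule, the plan would support two denominators and choose neither in advance.

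**Conclusion.** The point holds for formal withdrawals on all three benchmarks and, for willingness, extends to anyone not reached at 12 weeks, whose place in the denominator is undefined. Because withdrawal is likely to be related to low acceptability, the figures will tend to favour the program; unrelated withdrawals can act the other way.

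On the willingness bar, excluding 10% to 30% of the arm reduces the positives required from 83% to between 73% and 57% of those randomised. The session bar reverses at around 20% withdrawal under the completion rates assumed, and not at 10%. These sizes assume 30 in Activate and a withdrawal rate that the documents do not give. No efficacy estimate is affected. The plan should be changed because the benchmarks are declared in advance as the rule for leaving the program unrevised.

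**What to change.** In Statistical Considerations, define each benchmark over all adolescents randomised to Activate, and say whether the session and goal percentages are pooled or per person.

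- Sessions: out of 8 for every participant.
- Goals: out of all goal days or weeks in weeks 2 to 12, with those after stopping counted as not met. Counting days or weeks avoids inventing personalised targets for someone who has left.
- Willingness: absent feedback counts as not positive in the main figure. Show the responder-only figure and the retention rate beside it.

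In Withdrawal Procedures, state that data collected before withdrawal are kept for Aim 1a. Reconcile that section with the all-participants statements in the protocol's efficacy paragraph and in the SAP.

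Asking those who leave the willingness question when they stop would help, but it is optional and subject to consent, as is keeping their earlier data; the consent text is not among the documents available here.

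The cost is a few sentences of protocol text. The figures will be somewhat less favourable, and non-response for unrelated reasons will count against the program. The responder-only figure shows how much of the shortfall is due to absence.

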Glucose meter and insulin rate reporting: The research assistant will provide instructions for the participant to report readings from their diabetes devices. For continuous glucose sensor and insulin pump users, device data for the past month will be provided through data exports from the device software for sharing with healthcare teams, with no medical device ID or personal identifiers retained. For glucose meter users, they will report glucose readings for the last 7 days from their glucose meter. For insulin injection users, they will report long-acting insulin doses and carbohydrate exchange ratios used over the last 7 days.

As the final activity of the baseline assessment, the participants will be randomized to the Activate program or treatment-as-usual and receive instruction, if required on completing the intervention program, and for all the follow-up assessment.

After twelve weeks, adolescents and their primary caregiver will repeat the entire baseline assessment battery in a second video-based lab appointment. Adolescents will receive \$25 for the intake assessment and \$50 for the follow-up assessment on a study provided cash card or gift card. Adolescents will return the assessment toolkit with a pre-paid mailing label.

Intervention: Activate Program

Adolescents randomized to the active condition will participate in a 12-week online diabetes behavior-change skills training and physical activity promotion program. See attached intervention guide for protocols beyond description below.

Diabetes Behavior-Change Skills Training. Behavior-change skills training will be provided through eight web-delivered content and activity sessions across the 12-week program. Sessions 1 through 4 will occur weekly and sessions 5 through 8 biweekly. Each session takes approximately 15-20 minutes for the adolescent to complete both content learning and related activities. Session 1 (week 1 of program) provides an introduction to the entire Activate Program as well as a goal-setting activity related to type 1 diabetes management. Sessions 2-8 (weeks 2 to 12 of the program) provide physical activity reminders that overlap with text-based support for the physical activity program (see below) as well as specific session content for behavior-change skills training: goal setting, goal planning and rewards, identifying challenges, problem-solving, increasing social support and positive activities, and managing strong emotions.

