Physical Activity Incentives Program. The physical activity incentives program includes 12 weeks of personalized goals and incentives for increasing physically active minutes along with weekday text-based support. Active minutes, defined as minutes with moderate to vigorous physical activity, will be tracked via a Garmin fitness activity tracker, which is synced to a coded study-specific account via PhysioQ's Labfront, a secure site used to collect and manage Garmin fitness activity tracker data. All data will be deidentified and only accessible to the research team. In week 1, all adolescents will receive incentives for syncing their Garmin fitness activity tracker on at least five days. In weeks 2 to 12, adolescents will receive personalized daily and weekly activity goals based on their progress. Daily incentives will be offered for meeting daily goals, and increased earnings will be available for meeting weekly bonus goals. Maximum earnings across the 12 weeks will be \$430. Weekdays, text-based support will be provided to remind adolescents of goals and earning potential as well as additional support to problem-solve technology and physical activity difficulties when indicated. Education prior to the intervention will follow American Diabetes Association³¹ guidance including information about how insulin requirements change with increased physical activity and how to prevent hypo and

hyperglycemia during and after exercise as well as reviewing the adolescent's plans for managing low blood glucose and contacting their pediatric endocrinologist with questions about glucose management with increased physical activity. All incentives will be delivered weekly on a cash card provided by the study or via gift card(s) provided at an interval chosen by the participant.

Treatment-as-Usual Control condition. For those in treatment as usual, participants will be trained to wear a Garmin fitness activity tracker daily for the next 12 weeks and asked to follow their standard care for diabetes management.

Describe required screening procedures performed before enrollment and while on study.

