Behavior-Change Skills. We will use two measures to assess key behavior-change skills taught in the intervention program: goal setting and coping skills. Adolescents' goal setting will be assessed using a procedure by Karoly et al. (2005) that was validated for use with adolescents with type 1 diabetes.^{65,66} Participants will be asked to identify their most important diabetes, academic, social, and career/family goals. Following this, participants will be asked to identify which of their three non-diabetes goals most interfered with their diabetes goal. Participants will also complete the four-item planning subscale from the Goal System Assessment Battery⁶⁵ to determine goal-directed planning activity related to the diabetes goal identified in the goal assessment. Average levels of goal-directed planning will be used as the outcome variable for goal setting. Adolescents' coping skill self-efficacy will be assessed using the Coping Self-Efficacy Scale, a 26-item measure that indexes participants confidence in using different strategies to cope with challenges in daily life.⁶⁷

Active minutes. We will use Garmin fitness activity tracker tracking to determine the average number of daily minutes with moderate to vigorous physical activity, metabolic equivalents (METs) greater than or equal to 3 METs, in week 1 and week 12.

Secondary Biobehavioral Self-Regulation Mechanisms

2. **Self-Report Assessment of Behavior Regulation and Distress:** The self-report tasks will be completed via questionnaires linked only to study ID on RedCap with the access link provided by the research assistant. When noted the parent will also report on their perception of their child's functioning in that domain.

Self-Regulation. We will use the following measures to assess regulation generally and in the diabetes context.

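### The multilevel gain-score model is ANCOVA in effect: likelihood cannot recover missing week-12 values, the SAP replaces them with zeros, and tracker weeks 2–11 stay outside the efficacy model

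*Protocol*

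**What the plan says.** **Model.** The protocol (Statistical Considerations, Aim 1) states: "We will conduct multilevel models with baseline-residualized gain scores for outcomes to identify the effect size". The SAP repeats it: "We will conduct multilevel models with baseline- residualized gain scores for outcomes". The protocol adds the baseline outcome, diabetes technology use and time since diagnosis as covariates; the SAP lists none. Neither document names a level, a random effect or a cluster.

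**Time points.** Outcomes are "compared between treatment and control groups at baseline and the 12-week follow-up assessment". Active minutes (Primary Outcomes) are averaged over days of activity "greater than or equal to 3 METs, in week 1 and week 12". The questionnaires are given at two visits: "After twelve weeks, adolescents and their primary caregiver will repeat the entire baseline assessment battery".

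**Tracker.** In the control arm, "participants will be trained to wear a Garmin fitness activity tracker daily for the next 12 weeks". The Activate arm is tracked over the same 12 weeks for the incentives programme.

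**Missing data.** There are three rules. The protocol says: "All participants will be used in analyses, with missing data addressed with full information maximum likelihood estimation". The SAP, whose only primary outcome is active minutes, enters a zero for missing data and calls this intention to treat. The protocol's Withdrawal Procedures leave participants who withdraw, or are withdrawn, out of the analyses.

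**The concern.** A residualised gain reduces each adolescent to one number, so a second level has nothing to estimate and the analyst must decide what was meant. The missing-data wording has more practical weight. An adolescent with no week-12 value has no gain, and likelihood can help only if the model contains something that predicts the missing value, such as the intermediate weeks. The plan collects those weeks and leaves them out of the efficacy model. If less active adolescents stop wearing or syncing the tracker, completers give a biased effect and fewer data. Zero-filling keeps everyone in the analysis but records a tracker that was not worn as no activity. The three rules can give three different answers for the same outcome.

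**Working it through.** **Inputs.** From the documents: 60 adolescents, one week-1 and one week-12 value, 12 weeks of tracking, d = 0.6, 0.7 and 0.8. Assumed, because not stated: 30 per arm, two-sided 5%, all dropout rates and all correlations.

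**1. The plan's own power figures.** The plan gives 60%, 80% and 95% at d = 0.6, 0.7 and 0.8. A two-sample t-test with 30 per arm gives 62.8%, 76.0% and 86.1%. The figures do not reproduce. That is a separate matter, and nothing below depends on it.

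**2. No second level.** With one score per person, y = mean + u + e, and the likelihood depends only on the sum Var(u) + Var(e). In a simulated trial the log-likelihood was −247.974 whether u took 0%, 30%, 60% or 90% of the variance.

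**3. The model is ANCOVA.** The residualised gain is R = Y − (a + bX), where X is baseline. Regressing R on arm and X differs from regressing Y on arm and X only in the intercept and the X slope, so the arm coefficient is the same: 11.3853 both ways in the example. Without the baseline covariate, which the SAP does not list, it was 11.3807.

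**4. Likelihood uses completers only.** Write f(X, Y | arm) = f(X | arm) × f(Y | X, arm). Someone without Y contributes only to the first factor, and the treatment coefficient sits in the second. With 19 of 60 missing week 12, joint maximum likelihood and complete cases both gave 11.7748. At d = 0.7, unadjusted power falls from 76.0% with 30 per arm to 71.4%, 66.1% and 60.0% with 27, 24 and 21 per arm (10%, 20% and 30% dropout).

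**5. Zero-filling.** The expected difference is (1 − m_A)μ_A − (1 − m_C)μ_C, where m is the fraction missing and μ the mean in the Activate (A) and control (C) arms.
- No true effect, an illustrative 30 min/day in both arms, 20% missing in Activate and 10% in control: 0.8 × 30 − 0.9 × 30 = −3 min/day. With the rates reversed it is +3.
- 20% missing at random in both arms: the true difference is multiplied by 0.8.

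The distortion can go either way. Power need not fall, because better retention in one arm is counted as activity.

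**6. Adding weeks 2–11, dropout unrelated to activity (d = 0.6).** Adjusted for week 1, the completers' variance is 2(1 − ρ²)/[30(1 − m)]. With constant correlation ρ = 0.5 and m = 0.2:
- Completers: 2 × 0.75/24 = 0.0625, SE 0.25, power Φ(0.6/0.25 − 1.96) = Φ(0.44) = 67.0%.
- Weekly model, relative efficiency 1.045: variance 0.0625/1.045 = 0.0598, power 68.9%.

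Five correlation structures were tried (constant 0.5 and 0.7, AR(1) 0.7 and 0.9, and a mixture). Relative efficiency was 1.00 without dropout, 1.02–1.07 at 20% and 1.04–1.11 at 30%. Power rose by 0.9–2.7 and 1.3–4.3 points, and by about 2 to 4 points in most settings.

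**7. Dropout likelier after low-activity weeks (d = 0.7, random intercept plus AR(1), covariance estimated, week 1 equal by arm).** Simulation put the weekly model 4–9 power points above completers at about 20% dropout and 8–11 at about 33%. A repeat with 600 trials per setting (Monte Carlo error about 2 points), random-intercept share 0.3 or 0.5 and AR(1) 0.6, gave 3–6 points at about 18% and 6–7 at about 30%. In it, completers estimated d at 0.65–0.66 against a true 0.7.

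**8. Baseline adjustment must be kept.** With complete data, an unconstrained arm-by-week model estimates the raw week-12 difference, with variance 2/30. ANCOVA has (1 − r²) × 2/30. At d = 0.7 that is 76.0% power against 79.8% (r = 0.3) or 86.8% (r = 0.5), a loss of about 4 to 11 points.

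**The case against.** The best defence is that the label does no harm. A reader might infer that the primary analysis cannot be fitted. The documents do not support that: only the surplus variance is unidentified, the treatment effect is estimable, and ANCOVA is a sound choice. This stands.

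A reader might also infer that the whole plan falls back to complete cases. For active minutes the SAP zero-fills, so everyone has a score. The completers-only result belongs to the protocol's rule. This stands too, but zero-filling is a different defect, not a remedy.

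A third reading is that ten weeks of data are wasted. In the Activate arm they drive incentives and the goals-met acceptability benchmark, and choosing week 12 as the endpoint is legitimate. They are absent only from the efficacy model.

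Finally, the weekly model has its own weak point. Randomisation closes the baseline visit, so week 1 falls inside the programme, with Session 1 and syncing incentives, although personalised activity goals start in week 2. If the arms already differ at week 1, constraining them equal shifts the week-12 estimate by roughly the week-1 difference times the week-12-on-week-1 slope. The present gain score has the same weakness. This objection stands and shapes the fix.

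**Conclusion.** The point holds in this form. The stated model is ANCOVA with an unidentified extra variance. The protocol's claim that likelihood brings in all participants is not delivered by a model with one follow-up value. The SAP's zero rule distorts active minutes, and the withdrawal rule conflicts with both.

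The size is modest and conditional. Against completers, the weekly model gains nothing without dropout, about 1 to 4 power points at 20–30% dropout unrelated to activity, and about 4 to 11 at 20–33% activity-related dropout. The repeat simulation gave 3 to 7, so the upper end is not secure. All of this rests on assumed dropout and correlations, and on week 1 being equal by arm. The documents do not support a claim of a large, certain gain. The firmer reason to change is that one coherent missing-data model would replace three conflicting rules. The unused-weeks point applies to active minutes only, since goal planning and coping are measured twice.

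**What to change.** 1. **Active minutes.** In both documents, replace the residualised-gain, full-information and zero-fill wording with one likelihood-based repeated-measures model of the weekly averages for weeks 1–12. Include arm-by-week effects and the disease covariates, and take the week-12 arm contrast as the primary estimate. Prespecify a parsimonious covariance, for example random intercept plus AR(1). Constrain the arms equal at week 1 to keep the baseline adjustment, and do not also enter week 1 as a covariate. State that week 1 falls after randomisation, and report a sensitivity analysis without the constraint. Define which days count towards a weekly average, so that non-wear does not return as zeros.
2. **Outcomes measured twice.** Call the analysis ANCOVA, and do not claim that likelihood recovers missing follow-up.
3. **Consistency.** Reconcile the protocol's Statistical Considerations and Withdrawal Procedures with the SAP, so that data collected up to withdrawal are used.

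The cost is wording in two documents and some programming; the data are already being collected. The downside is that a weekly covariance structure must be chosen in advance for 60 participants.
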